Botulinum Toxin to improve cosmesis of primary cleft lip repair

NCT02247193

Version Date: 02/17/2015

Protocol Title: Botulinum Toxin to improve cosmesis of primary cleft lip repair

Principal Investigator: [name], MD

Primary Mentor: [name], MD

Additional Investigator: [name], MD

Co-Mentor/Preceptor: [name], MD

Population: Pediatric patients requiring a primary cleft lip repair younger than 6 months of age.
Goal of 40 patients total enrolled.

Number of Sites: UT Health – Memorial Hermann Hospital – Texas Medical Center

Study Duration: 7/1/2014 – 6/30/2016

Subject Duration: From pre-operative assessment to minimum 1 year follow up

General Information

- Primary cleft lip repairs are most frequently done at 3 months of age. There are many factors that influence the final cosmetic appearance of the repair including wound tension. Unacceptable amounts of tension can lead to poor cosmetic appearance, wound dehiscence or fistula formation. Use of Botulinum toxin intraoperatively can reduce wound tension and therefore improve outcomes of cleft lip repairs.

Background Information

- Hypothesis: Utilizing Botulinum toxin intraoperatively during primary cleft lip repair will improve the cosmetic appearance of cleft lip scars. Patients with unilateral cleft lips with or without cleft palates will be considered.
- Few studies have been done utilizing botulinum toxin to improve outcomes of cleft lip repairs. Cleft lip repair outcomes are influenced by a number of factors including wound tension. Wound tension is often unavoidable in these patients due to continuous muscle contraction from crying or feeding. Therefore, limiting muscle contraction could potentially improve outcomes of these repairs. Tollefson et al. in 2006 reported the first study with targeted injections of botulinum toxin into the orbicularis oris in the cleft lip of patients younger than 6 months old. All three patients showed exceptional post-operative aesthetic outcomes at early follow up without any complications.
- The need to chemoimmobilize musculature associated with cleft lip repair is of even greater importance as multiple studies have shown increased activity of these muscles. Carvajal et al. established that orbicularis oris activity was significantly greater in cleft lip and palate patients than those children without clefts. Aside from the impact this can have on the growing maxilla this increased muscle activity can be problematic for cleft lip repair cosmesis.
- In 2009, Galárraga used intraoperative botulinum toxin on 5 patients all younger than 6 months of age undergoing a primary cheiloplasty. The study showed the botulinum toxin injections to be safe without any complications observed. An EMG proven decrease in muscle activity around the repair site was also seen as predicted.
- Studies in adult patients have shown improved cosmetic outcomes for facial wounds when utilizing botulinum toxin. They have also established use of the toxin as safe in the face. Ziade et al. in 2013 showed injections of botulinum toxin type A within 72 hours postoperatively around facial wound repairs had better scar results at 1 year follow up as analyzed by 6 expert specialists. Wilson in 2006, showed utilization of botulinum toxin in revision facial scar surgery had 90 % of patients with a highly satisfactory outcome.

Objectives

Improve cheiloplasty outcomes with the use of intraoperative injection of botulinum toxin to clefted lip.

Study Design

- Randomized double blinded controlled trial of pediatric patients who require a primary unilateral cleft lip repair younger than 6 months of age. Utilization of botulinum toxin intraoperatively at targeted locations of the cleft lip. Surgeon, parents and expert panel of surgeons used at the completion study will all be blinded to which patients received the experimental injection.
- Control subjects will receive injections of normal saline at identical sites of the cleft lip as experimental subjects.
- 20 patients in each group will be enrolled.
- Patients will be evaluated preoperatively, postoperatively at 1 week, 1 month, 3 months, 6 months and 12 months of follow up.
- **Inclusion criteria:** Unilateral cleft lip with or without cleft palate, less than 6 months of age
- **Exclusion criteria:** Bilateral cleft lip, older than 6 months of age
- Primary endpoint: Blinded assessment of wound cosmesis by plastic surgeons and parents using scar assessment scale. At completion of follow up use of aesthetic grading criteria of videography images as described by Reddy et al. in 2008. These criteria include: Matching accuracy of white roll and vermillion border, scar appearance, Cupid's bow form, length of lip, nostril symmetry, alar dome form, and alar base position

Study Population

- Pediatric patients with complete unilateral cleft lip and palate less than 6 months of age undergoing cleft lip repair.
- All patients who will be planned for a primary cleft lip repair will be offered to be enrolled in the study. Parents may choose to decline and undergo repair without enrollment in the study.
- Patients will be recruited as they would present otherwise to the University of Texas Pediatric Plastic Surgery Clinic to be evaluated for repair of cleft lip.

Study Procedures

- Patient will receive intraoperative botulinum toxin injections in the upper labial musculature prior to the operative repair being started.
- 4 injection sites will be used two superior and inferiorly in the cleft lip, 1 unit of botulinum toxin per injection site to be used. This is considered low dose in the pediatric population. Depending on the patient's weight it will be approximately 1 unit/kg.
- This dosing was chosen as it has been proven safe without any complications in prior pediatric botulinum toxin studies.
- This dosage has also been shown to adequately elicit muscle paresis in the head and neck.
- Patients will have videography performed preoperatively as well at scheduled post-operative visits.
- Parents will complete a Modified Vancouver Scar Scale at selective post-operative visits
- The Vancouver scar scale is a widely used validated scar scale for adults, however given our study it was modified appropriately for pediatric populations. There is no validated scar scale for pediatric patients.
- At the completion of the 1 year follow up period, videography will be sent to an expert panel of select plastic surgeons that will also use the Modified Vancouver Scar Scale to assess scar outcomes in both the control and experimental groups. This panel will be blinded to which patients received botulinum toxin and which received the control injection.
- Videography at the completion of the study will also be assessed for the following measures: Matching accuracy of white roll and vermillion border, scar appearance, Cupid's bow form, length of lip, nostril symmetry, alar dome form, and alar base position. Study personnel will be blinded to which patients received the experimental injection.
- No invasive procedures or postoperative monitoring will be employed unless deemed medically necessary.

Block Randomization

Block randomization will be used for this study. The size of the blocks will not be fixed to ensure surgeons are truly blinded along with each arm of the study having the same number of patients. Therefore each group may have block sizes of 3, 5, 2, 6 and 4 to allow for a total of 20 patients. Both the ordering of blocks and their respective size will be blinded to eliminate any selection bias.

Drug Administration and Accountability

[name] MD, [name], MD and [name] will be responsible for botulinum toxin accountability. The toxin will be stored with the operating room pharmacy. As the study will be a randomized controlled trial, for those patients set to receive botulinum toxin, the medication will be requested from the OR pharmacy on the day of surgery. Prior to surgery it will be ensured the OR pharmacy has the toxin available. The toxin will be mixed as prescribed and 1 unit injections at 4 distinct sites will be used for a total of 4 units administered.

The pediatric plastic surgery research nurse will be responsible for notifying the operating room circulator whether that day's block of patients will be receiving the experimental versus the control injection.

Study patients will be attempted to be scheduled on the same OR days to maximize utilization of each botulinum toxin vial as they have a limited shelf life once mixed. Once the vial has been utilized it will be dispensed appropriately. The vials in the OR pharmacy will be stored in a standard cooled refrigerator as recommended by the manufacturer.

Possible Risks to Subjects

- Botulinum toxin safety has been well established. The FDA endorses that botulinum toxin use in a dermatologic fashion have no reported adverse side effects at the recommended doses. Studies which have utilized botulinum toxin in patients younger than 6 months of age have not reported significant adverse effects.
- Transient fatigue lasting no longer than 96 hours has been noted in a study by Pascual and Pascual in 2008 in one patient out of 74.
- The likelihood of risks are low and most studies have shown no side effects while few studies have noted transient fatigue in less than 5% of patients.
- Given that botulinum toxin takes 72 hours minimum to take effect there will be no change in the surgical procedure. Therefore there is no significant change in risk of the surgery itself.
- Also of note this study will be using botulinum toxin doses lower than most studies already completed, therefore the risk should be less as the risk of botulinum toxin is dose dependent.
- Two prior cleft lip studies utilizing botulinum toxin reported good outcomes with no complications or feeding difficulties.

Rare reported adult adverse side effects of botulinum toxin include: Difficulty swallowing, breathing, speaking, feeding, diffuse muscle weakness, double vision, voice changes, allergic reaction and bladder dysfunction. However, no documented adverse effects have been noted when used at dermatologic doses on the face.

Safety

- Two studies on cleft lip patients younger than 6 months of age utilizing botulinum toxin have been completed without any complications and shown the toxin to be safe in this population.

Prior cleft specific studies

- Tollefson et al. in 2006 with 3 patients and Galarraga in 2009 with 5 patients used botulinum toxin injections in the cleft lip without any reported complications.

Prior pediatric botulinum toxin studies

- Botulinum toxin injections are also used for a large variety of pediatric conditions safely including ophthalmologic, gastrointestinal and neurological.
- Messner et al. in 2011 used 7 botulinum toxin injections in 3 patients younger than 6 months of age with for cricopharyngeal achalasia. Injections were done in the cricopharyngeus muscle with successful treatment allowing patients to eat by mouth as a result. No complications were encountered with an average follow up of 22 months, 3.3units/kg of botulinum toxin were used.
- Pascual and Pascual in 2008, reviewed botulinum toxin injection safety in patients younger than 2 years old. 74 patients received botulinum toxin injections with 28 younger than 1 year of age. Only 1 patient was noted to develop transient fatigue that lasted less than 4 days without intervention. All other patients did well with no significant adverse effects. On average 6.55 units/kg for patients less than 1 year of age and 8.4 units/kg in patients 1-2 years old were used. They deemed botulinum toxin injections safe at the appropriate dosage.
- Chhina et al. in 2013 showed higher dosages of botulinum toxin were safe in patients less than 2 years of age. Injections were done in the feet on patients with clubfeet. 239 patients and 361 feet were injected with 10 units/kg. No complications were noted in any patient and again deemed botulinum toxin injections safe.
- Oleszek et al. in 2005 performed botulinum toxin injections for patients aged 6-18 months with congenital torticollis. 29.7 units of botulinum toxin were used on average for each patient. Only 2 patients had transient neck weakness with mild dysphagia that resolved without intervention. They showed that even at higher doses botulinum toxin was safe to use in the head and neck.
- Of note our study will only use a low dose of 4 units of botulinum toxin total and will approximately be 1 unit/kg dosing depending on the weight of our study patient. This dosage is less than most pediatric botulinum toxin injection studies to date and therefore should be a safe dosage.
- As noted above a large number of studies have shown botulinum toxin to be safe at both low and high doses at a variety of anatomic locations including the head and neck.

Safety Monitoring

The PI, co-investigator and mentor will review any reported adverse events monthly.

- Patients feeding capabilities, respiratory status, neuromuscular function and overall health will be evaluated on each scheduled follow up visit.

Statistics

- Using the Modified Vancouver Scar Scale we hypothesize the average score for controls to be 7 out of 11. For experimental patients we expect an average score of 10 out of 11. Given a 90% confidence interval and standard deviation of 2.5 the necessary sample size would be 15 subjects per group using a 2 sided test.
- Therefore 20 patients will be the goal group size for each arm of the study; botulinum toxin injection group versus control group.
- The study will be terminated if any subjects display significant adverse side effects that are potentially life threatening including feeding, cardiovascular or respiratory complications.
- Study subjects to be used will be all patients who will undergo a primary cleft lip repair that agree to participation in the study and subsequent randomization.

Ethics

- Prior to initiating the study University of Texas Health Science Center at Houston Institutional Review Board will need to grant approval for the study.
- Consent will be obtained in person at the time of the pre-operative visit in the University of Texas Pediatric Plastic Surgery clinic. This consent will be in addition to the consent obtained for the surgical procedure. The known risks and adverse effects of botulinum toxin will be fully disclosed to parents prior to obtaining consent for the study.

- Consent will also be required to be obtained for videography that will be used pre/post operatively to evaluate cosmesis of the repair.

Data handling and record keeping

- Operative reports will be securely located in the Care4 EMR of Memorial Hermann Hospital which is the hospital affiliated with the University of Texas Medical School at Houston where the cleft lip repairs will occur.
- All data will be securely located on a LOK IT secure flash drive as approved by the University of Texas Medical School at Houston. LOK IT secure flash drive is password coded and identified as a suitable way to store patient sensitive data.
- Videography will also be kept on this secure LOK IT flash drive to ensure confidentiality.
- A computer supplied and maintained by the University of Texas Medical School at Houston that is in the Otolaryngology resident work room will be the main computer used when accessing and analyzing data/images. The computer is password protected and is approved for use by the medical school for data collection use.
- Images of the patient will only include the face to assess the outcomes of the repair. All images taken at planned post-operative visits will be taken with the same camera and calibration settings.
- Data and images will be coded by a discrete number that will be used to identify an individual patient and their repair. No patient identifiers will be linked to the videos

Quality control and assurance

- Videography camera will be operated by a select number of users that have been taught the appropriate amount of training to operate it appropriately.
- Camera will be calibrated prior to each session to ensure consistent videography.
- A modified Vancouver Scar Scale will be given to parents at post-operative visits.
- Botulinum toxin will be prepared in the same manner for each patient.

Publication Plan

- Plan to submit abstract and manuscript to reputable conferences and otolaryngology journals at the completion of the study.

ATTACHMENTS

1. Study Schedule
2. Consent Document
3. Modified Vancouver Scar Scale
4. Aesthetic grading criteria table

REFERENCES

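### The primary endpoint names two raters and adds an aesthetic grading, but no visible text says whose score decides the trial, and the sample size names neither rater nor visit

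*Combined protocol and SAP*

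**What the plan says.** **Endpoint.** The Study Design section has a single bullet for the primary endpoint: "Primary endpoint: Blinded assessment of wound cosmesis by plastic surgeons and parents using scar assessment scale". The bullet goes on to an aesthetic grading of the video images at the end of follow-up: "These criteria include: Matching accuracy of white roll and vermillion border, scar appearance", followed by five more items, seven in all. Nothing calls this grading secondary.

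**Who rates, and when.** Study Design gives the visits: "Patients will be evaluated preoperatively, postoperatively at 1 week, 1 month, 3 months, 6 months and 12 months of follow up". Study Procedures then describes three sets of ratings:
- Parents: "Parents will complete a Modified Vancouver Scar Scale at selective post-operative visits". Quality control and assurance also places the parent form at postoperative visits, again without naming any.
- Surgeons: "At the completion of the 1 year follow up period, videography will be sent to an expert panel of select plastic surgeons", who score the same scale.
- Aesthetic grading: "Videography at the completion of the study will also be assessed for the following measures", followed by the seven items.

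**Sample size.** The Statistics section says "Using the Modified Vancouver Scar Scale we hypothesize the average score for controls to be 7 out of 11", expects 10 in the experimental arm, and continues: "Given a 90% confidence interval and standard deviation of 2.5 the necessary sample size would be 15 subjects per group", two-sided. The enrolment goal is 20 per arm. The section names no rater, visit, test statistic, success rule or multiplicity control.

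**The concern.** A primary endpoint should lead to one decision. Here two groups of people score the same scale, and a second instrument stands in the same bullet. If the panel favours botulinum toxin and the parents see no difference, or the reverse, the plan does not say whether the trial was positive. The favourable measure could then be chosen once the results are known.

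The sample-size statement does not close the gap. It points to the Modified Vancouver Scar Scale, but parents and panel both complete that scale, so the assumed means of 7 and 10 belong to no identified score.

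Timing is also partly open. The parent visits are not named. For the panel and the aesthetic grading, the text says when the videos are sent or assessed, but not which visit's video is rated, and videos are taken before surgery and at the scheduled postoperative visits.

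**Working it through.** **Inputs from the Statistics section.** Control mean 7, experimental mean 10, so the difference is 3. SD 2.5, so the standardised difference is 3/2.5 = 1.2. Two-sided, 15 per group needed, 20 per group planned. Power is not stated.

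**Assumed here.** The correlation between measures (0 to 0.9), because the documents give none. Each decision rule below is also an assumption, because the plan gives none.

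**1. Reproducing the plan's figure.** For one comparison of two means, n per group = 2(z_alpha/2 + z_power)² / 1.2².
- Two-sided 0.05, 90% power: 2(1.960 + 1.282)² / 1.44 = 14.59, so 15.
- Alpha 0.10, 90% power: 2(1.645 + 1.282)² / 1.44 = 11.89, so 12.
- Alpha 0.10, 95% power: 2(1.645 + 1.645)² / 1.44 = 15.03, strictly 16.

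The stated 15 is therefore the size for a single comparison. It leaves no allowance for a second rater or a second instrument.

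**2. False-positive chance if any one result could count as success.** For independent tests it is 1 − (1 − alpha)^k. For correlated tests it comes from numerical integration of an equally correlated two-sided normal model.

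| Measures that could count | Nominal alpha | Corr. 0 | Corr. 0.5 | Corr. 0.9 |
|---|---|---|---|---|
| Two raters | 0.05 | 9.75% | 9.07% | 7.04% |
| Two raters plus one aesthetic total | 0.05 | 14.3% | 12.5% | 8.4% |
| Two raters | 0.10 | 19.0% | 17.6% | 13.6% |
| Two raters plus one aesthetic total | 0.10 | 27.1% | 23.6% | 15.9% |

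Check at correlation 0 and alpha 0.05: 1 − 0.95² = 0.0975 and 1 − 0.95³ = 0.1426. The 0.10 rows apply only if the 90% confidence wording is read literally.

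**3. False-positive chance if both raters had to agree.** Simulated two-sample t-tests, 20 per group, both significant at 0.05 in the same direction: 0.1% at correlation 0, rising to 2.9% at 0.9. Check at correlation 0: 0.05² / 2 = 0.00125.

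**4. Power under each rule that could be written in.** Standardised difference 1.2, assumed the same for each rater, normal scores. Noncentral t for single tests; simulation for both raters (correlation 0 to 0.9).

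| Rule | 20 evaluable per group | 15 evaluable per group |
|---|---|---|
| One primary at 0.05 | 95.9% | 88.7% |
| Both raters significant at 0.05 | 92-94% | 79-85% |
| Each rater at 0.025, per rater | 92.3% | 81.5% |

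Check for both raters at correlation 0: 0.9588² = 91.9% and 0.8872² = 78.7%.

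**5. Limit of the power model.** With mean 10 and SD 2.5, a normal model puts 1 − Φ((11 − 10)/2.5) = 1 − Φ(0.4) = 34% of treated scores above the maximum of 11. Real scores cannot follow that model, so step 4 is an illustration.

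**The case against.** The best defence is that the plan does lead with one instrument. The opening sentence of the bullet concerns the scar scale, the hypothesis concerns the appearance of the scar, the sample size uses only the Modified Vancouver Scar Scale, and Study Procedures introduces the seven measures as an additional assessment. Much of this stands: the aesthetic grading may well have been meant as supportive, and the rows above that include it rest on the weaker reading. The defence does not touch the choice between surgeons and parents, since both use the scale.

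The listed attachments (Study Schedule, scar-scale form, grading table) are not in the supplied text. The schedule may name the parent visits, and the table may define an aesthetic total, so those parts are not firm omissions. A success rule would normally be in the Statistics section, which is visible and has none.

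A reader might infer that the trial's error rate is inflated to 10% or more. The documents do not support that. They state no rule by which either rater counts, and under a rule that both must agree the rate falls below alpha. A reader might also infer that the panel's rating is firmly fixed at 12 months. That is the natural reading, but the text dates the sending and assessment of the videos, not the visit being rated.

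**Conclusion.** The concern holds, and it should be settled before unblinding, because what is undefined is the primary comparison itself. The firm gap is surgeon versus parent: neither is named as decisive, no rule covers disagreement, and no multiplicity control is visible. The place of the aesthetic grading and the rated visits are open to a lesser degree.

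At a nominal 0.05 the false-positive chance could lie anywhere from 0.1-3% (both raters must agree) to 7-10% (either suffices), or 8-14% if one aesthetic total also counted. These ranges rest on assumed rules and assumed correlations. They show how much depends on the missing rule and do not measure inflation in this plan. The arithmetic behind 15 per group is not at fault; it fits a single comparison that the endpoint bullet does not identify.

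**What to change.** **Name one primary comparison before unblinding.** For example: the mean across blinded panel surgeons of the Modified Vancouver Scar Scale score from the 12-month video, compared between arms with a two-sided test at 0.05. Make the parent score at one named visit and the aesthetic grading secondary. The documents would equally support parents as the primary rater, so the choice is the sponsor's. The sponsor may also keep both raters with a stated rule: both significant at 0.05, or each tested at 0.025. Name the same rater, visit and test in the Statistics section.

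**Cost.** Protocol wording only, with no added enrolment on the plan's own assumptions. The power of each option is in step 4 of the working; the two-rater rules lose more power if patients are lost before 12 months. The downside of a single primary is that a benefit seen only on a secondary measure could not be called a positive primary result.

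**Separate minor point.** Replace the 90% confidence interval wording with an explicit alpha and power. By the normal approximation, 15 per group matches two-sided 0.05 with 90% power, although a t-test needs 16. It also nearly matches alpha 0.10 with 95% power (15.03). The sponsor must say which was meant.

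### The plan relies on concealed block sizes but prints them, with the same list for each group, and describes a block as one day's patients; if any arm becomes known, other allocations may follow from it

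*Combined protocol and SAP*

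**What the plan says.** The trial is to randomise 40 infants, 20 per arm, with surgeon, parents and expert panel blinded (Study Design).

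The Block Randomization section gives the reason for varying the blocks: "The size of the blocks will not be fixed to ensure surgeons are truly blinded". It then lists sizes: "Therefore each group may have block sizes of 3, 5, 2, 6 and 4 to allow for a total of 20 patients". It closes with the safeguard: "Both the ordering of blocks and their respective size will be blinded to eliminate any selection bias".

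The next section, Drug Administration and Accountability, makes the research nurse responsible for "notifying the operating room circulator whether that day's block of patients will be receiving the experimental versus the control injection". On scheduling it says: "Study patients will be attempted to be scheduled on the same OR days to maximize utilization of each botulinum toxin vial". On supply it says that "for those patients set to receive botulinum toxin, the medication will be requested from the OR pharmacy on the day of surgery". No matching request is described for saline.

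Of the dose, Study Procedures says: "This dosage has also been shown to adequately elicit muscle paresis in the head and neck". Possible Risks to Subjects puts onset at 72 hours or later, and Study Design places the first postoperative visit at 1 week.

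**The concern.** Varying block sizes protect allocation when masking is imperfect. They do so only if staff cannot work out where a block begins and ends or what sizes are in use. Here the protocol names hidden size as its protection against selection bias, and two parts of its own text work against that.

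- The candidate sizes are printed in the protocol, and the list is the same for each group. If it is used as written, each size occurs once per arm, so two blocks of equal size are in opposite arms.
- A block is described as a day's patients on one injection type. When same-day scheduling succeeds, its size may be read off the operating list.

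Together these let knowledge of one arm spread to other infants, some not yet operated on. A person who can foresee an arm and also influences which infant goes on which day can influence allocation. An operating surgeon who foresees it is no longer blinded. The trial is small and its primary endpoint is a rating of appearance, so both matter.

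**Working it through.** **Inputs.** Sizes 3, 5, 2, 6 and 4 for each group (Block Randomization); 20 per arm and 40 in all (Study Design); one injection type per day's block (Drug Administration and Accountability).

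**1. The plan's own figure.** 3 + 5 + 2 + 6 + 4 = 20 per arm, and 2 × 20 = 40. The total is reproduced. Sizes 3 and 5 are odd and cannot be split 1:1, which fits blocks that hold a single arm.

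**2. Single-arm blocks, list used as written.** There are 10 blocks, five per arm, each size once per arm.

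- *Sizes only.* Without sizes, the ways to label five of ten blocks as toxin number C(10,5) = 252. With sizes, each equal-sized pair has one block in each arm, leaving 2^5 = 32. Each block is still toxin or control with probability 1/2, so no arm is identified.
- *One block's arm known.* The twin block of that size is then known too. Mean block size is 20/5 = 4, so with each block equally likely to be the one that leaks, the printed sizes expose on average 4 more infants (range 2 to 6). In random order the twin comes later half the time: 4 × 1/2 = 2 infants still to come, or 2/40 = 5% of the trial. A simulation over random orders gave 1.98.
- *The leaked block itself.* It also averages 4 infants, but they are exposed because a block holds one arm. That would happen whatever sizes were printed.
- *Worst case: all earlier arms known.* The second block of every size is certain: 3 + 5 + 2 + 6 + 4 = 20 of 40 infants. The first blocks remain at 50/50, so expected correct guesses are 20 + 20 × 1/2 = 30 of 40 (75%). For comparison, someone who knows the earlier arms and that there are five blocks per arm, but ignores size and guesses the arm with more blocks left, gets about 26.1 of 40 right (simulation).

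**3. Alternative reading: mixed blocks.** If the listed sizes are per-arm counts m, the blocks hold 6, 10, 4, 12 and 8 infants. In a balanced block of 2m, an observer who knows the size and the earlier arms is certain of 2m/(m + 1) allocations on average:

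| m | block | certain, 2m/(m + 1) |
|---|---|---|
| 3 | 6 | 1.50 |
| 5 | 10 | 1.67 |
| 2 | 4 | 1.33 |
| 6 | 12 | 1.71 |
| 4 | 8 | 1.60 |
| Total | 40 | 7.81 |

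That is about 7.8 of 40 (20%), with about 26.5 of 40 guesses correct (simulation). This reading sits poorly with the instruction that a day's block receives one injection type.

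**The case against.** The case on the other side has several sound parts.

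- *The list is conditional.* It says what sizes each group may have. If it is only an example, the twin-block figures do not apply. This stands, and every figure from single-arm pairs depends on it. But the protocol does not say that it is an example or that the real sizes are kept elsewhere.
- *Blinding order and respective size need not mean hiding the set of sizes.* On this reading staff merely do not know which block has which size. That is fair, and printing the set alone breaches little. The difficulty is the combination: once a block can be counted, the printed list turns the count into a pairing with another block.
- *Same-day scheduling is only attempted.* The study period is 24 months with at least 12 months of follow-up, leaving about 12 months to enrol 40 infants: 40/12 = 3.3 a month. A six-infant block would take 6/3.3 = 1.8 months to accrue. Blocks may therefore span several days, and a day's caseload would then not show the size. This stands as a limit on how often size is visible.
- *Other safeguards exist.* Every planned primary repair is offered entry, controls receive saline at identical sites, onset follows surgery by at least 72 hours, the panel is blinded and videos are coded. Nothing suggests that parents or panel would see block sizes. The exposure is therefore mainly in scheduling and in the operating room, not in the panel's ratings.

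A reader might infer that the sizes alone disclose the allocation, or that they account for all of the mean 8 infants identified when one block leaks. The documents support neither: sizes alone leave each block at 50/50, and 4 of those 8 are in the leaked block, exposed by single-arm blocks.

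**Conclusion.** The concern holds in a conditional form. The protocol weakens, by its own text, the concealment it relies on. No arm follows from sizes alone, and with perfect masking the harm is nil. The documents do leave routes by which an arm could become known: the circulator is told, toxin is requested on the day for toxin patients, and paresis may be visible from the first visit.

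Given one such leak, the loss attributable to the printed sizes is on average 4 further infants, about 2 of them still to come. This assumes that the list is the actual scheme, that blocks hold one arm and that their sizes can be seen. The figure of 20 of 40 is a worst case requiring knowledge of all earlier arms; 7.8 of 40 is its counterpart for mixed blocks. A reader might take 20 of 40 as the expected loss, but the documents do not show that any observer would hold that knowledge. The change should be made because it is cheap and removes a dependence on perfect masking.

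**What to change.** 1. Delete the block sizes from the protocol. State only that sizes are drawn at random and held in a restricted randomisation file, out of reach of those who recruit, schedule, operate or assess.
2. Redraw the sizes at random, and do not reuse the same set in each arm.
3. Randomise infants individually within blocks that contain both arms, and let blocks run independently of operating day. Removing the printed sizes alone would still let one leak expose a whole single-arm block.
4. Reword the nurse's instruction in Drug Administration and Accountability so that it refers to each infant's allocation and not to a day's block.

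The planned start is 7/1/2014 and this version is dated 02/17/2015, so enrolment may have begun; if so, the new list applies to infants not yet randomised.

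The cost is a few sentences of protocol text and a redrawn list. Arms may be slightly unequal if enrolment stops mid-block. Vial sharing becomes somewhat less efficient, because infants operated on the same day will not all be in one arm.
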